9.7.3.2. RZV ≥ 1 Dose Analysis

The RZV ≥ 1 dose analysis will be used to assess the secondary objectives for effectiveness and safety. Incidence rates and corresponding 95% confidence intervals for the primary (HZ) and secondary (disease flare) outcomes will be calculated before and after weighting in each of the 4 RZV ≥ 1 Dose and Comparator ≥ 1 Dose cohorts. All analyses will be performed separately within the UC and RA cohorts. The incidence rate of each outcome in the RZV ≥ 1 Dose cohort will be compared to the Comparator ≥ 1 Dose cohort. Weighted Kaplan-Meier plots will be used to depict the cumulative probability of survival (non-occurrence of the event).

As in the RZV 2-dose analysis (Section 9.7.3.1), we will calculate the number of patients that were selected and included in a study cohort more than once. If that number exceeds 10% of the study population, then covariance between observations will be taken into account using an appropriate method (eg, generalised estimating equations or robust variance estimators).

The relative hazard will be calculated through weighted Cox regression models with appropriate 95% confidence intervals. Known confounders that are strongly associated with receipt of at least one RZV dose and the study outcomes may also be included in the regression models as well as any variables with an absolute SD >0.1 between weighted exposure cohorts. Additional details on model selection will be detailed in the SAP

9.7.4. Sensitivity Analysis

For sensitivity analyses, Optum will investigate alternative eligibility requirements of tofacitinib exposure, including the creation of a separate set of RZV 2-Dose, RZV ≥ 1 Dose, and matched comparator cohorts that include current tofacitinib users and recent tofacitinib users within given time intervals, such as 8 weeks, preceding cohort entry. The inclusion of recent tofacitinib users will maximize sample size while allowing for observation of study outcomes among patients with tofacitinib treatment spanning both RZV doses as well as those patients with tofacitinib treatment overlapping with only one of the RZV doses. This approach will allow for the evaluation of effectiveness and safety across a range of real-world use patterns and address the potential for extended immunosuppressant effects of tofacitinib following discontinuation. Recent tofacitinib users will be identified as patients who met the current user definition within the past 8 weeks (or other specified time interval). A tofacitinib recent-treatment period will be defined as starting on the day following the end of the on-treatment period (ie, end of tofacitinib days' supply plus a 30-day grace period) and continue for a duration of 8 weeks. Depending on sample size, periods of recent use shorter or longer than 8 weeks may be considered. In this sensitivity analysis, patients who receive a second dose of RZV with the second dose occurring during a tofacitinib on-treatment period or 8-week recent-treatment period on or after the study initiation date will be included in the RZV 2-Dose cohort. Similarly, patients who receive a first administration of RZV during a tofacitinib on-treatment period or a tofacitinib 8-week recent-treatment period on or after the study initiation date, with no administration of RZV in the prior 365 days, will be included in the RZV ≥ 1 Dose cohort. Each of the RZV cohorts will be time-matched to comparators who also meet the definition of current or recent user of tofacitinib. This analysis will

include the 2-dose and ≥ 1 dose analyses for primary and secondary outcomes.

In addition, using the main study cohorts, Optum will consider applying a more restrictive definition of current tofacitinib exposure (ie, not including the 30-day grace period when identifying current tofacitinib users), and according to cumulative tofacitinib dose. To assess a potential dose-response relationship between tofacitinib exposure and study outcomes, a sensitivity analysis will be performed in which the cohorts are stratified based on tofacitinib dose. Specifically, the daily dose of tofacitinib will be calculated based on dispensings received in the 91 days prior to cohort entry and then the cohorts will be stratified according to high versus low dose of tofacitinib based on the median daily dose. In addition, the cohorts will also be stratified based on cumulative dose of tofacitinib received in the 365 days prior to cohort entry. As patient follow-up will not be censored upon discontinuation of tofacitinib treatment, a sensitivity analysis will be conducted in which patients are stratified based on continued exposure to tofacitinib during follow-up.

As the study period includes time before and during the COVID-19 pandemic, a sensitivity analysis will be conducted stratified by calendar time (cohort entry prior to 20 January 2020 and cohort entry on or after 20 January 2020).

A quantitative bias analysis will also be performed to assess the potential magnitude of bias due to unmeasured confounding, including confounding by incompletely captured or missing covariates (eg, UC/RA severity). A standard epidemiological spreadsheet will be used to assess the robustness of the results in the presence of an unmeasured confounder.³⁴ The results of the main analyses for the association between RZV exposure and the primary and secondary outcomes along with varying magnitudes of the confounder-outcome association and confounder-RZV association will be used to calculate the difference from the observed findings after accounting for the unmeasured confounder. The range of associations to be applied for the confounder-outcome and confounder-RZV associations will be informed by published literature and associations observed for related variables in the current study.

As patients that have UC and RA may have different clinical characteristics compared to patients that have only one of the two diseases, the number of patients that have both diagnoses will be quantified. Additionally, a sensitivity analysis will be conducted in which the association between RZV exposure and the primary and secondary outcomes is assessed after excluding patients with both UC and RA from the exposure cohorts.

To assess the effect of prior Zostavax vaccination on subsequent RZV effect, an analysis will be performed where the study population is restricted to patients with at least 5 years of enrollment prior to cohort entry. Within this subset, the analysis will be conducted separately among patients with and without Zostavax vaccination during this baseline 5-year period. The effect of prior Zostavax exposure will be informed by the extent to which the estimate of RZV effect differs according to strata of prior Zostavax exposure.

It is possible that the comparator cohorts could include patients previously vaccinated with RZV more than 365 days earlier. To address this potential exposure misclassification, a sensitivity analysis will be performed, for which the study population will be restricted to patients with enrollment that extends back to 20 October 2017 and who do not have any prior administration of RZV during that time. Finally, a sensitivity analysis will be conducted for HZ in which patients are stratified based on their amount of available follow-up time.

Misclassification of disease flares is possible when using claims-based algorithms (for example, patients may change therapy for reasons other than disease flares), leading to over- or under-estimation of the outcome; thus, alternative definitions will be explored and outlined in the SAP as sensitivity analyses. Specifically, sensitivity analysis will explore using a more conservative definition based on only UC-related surgeries or ER and hospitalizations with UC or RA as the primary diagnosis, as well as evaluating more expansive definitions inclusive of other medications of interest, such as biologics or other JAK inhibitor treatments.

Additional sensitivity analysis may be performed if needed.

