7. RATIONALE AND BACKGROUND

Tofacitinib (Xeljanz[®], Pfizer Inc., New York, NY) is an oral Janus kinase (JAK) inhibitor with multiple indications, including for individuals with moderately to severely active ulcerative colitis (UC) or rheumatoid arthritis (RA) who have had an inadequate response or intolerance to one or more tumor necrosis factor (TNF) blockers. UC, a type of inflammatory bowel disease (IBD), is an autoimmune condition involving chronic inflammation of the mucosa of the rectum and colon, clinically characterized by bloody diarrhea and abdominal pain.¹ Rheumatoid arthritis (RA) is an autoimmune condition involving chronic localized and systemic inflammation, with inflammation of the joints leading to erosion or destruction of joint structures, affecting function, and leading to progressive disability.² Patients who have UC or RA are at increased risk of infections, including herpes zoster (HZ), due to the underlying autoimmune condition, and also as a consequence of treatment with immunosuppressant therapies.^{3,4} Increased rates of HZ have been observed in patients treated with tofacitinib compared to patients receiving placebo.^{5,6} Consequently, HZ is among the infections included in the Warnings section in the prescribing information for tofacitinib.⁷

Shingrix[®], a recombinant zoster vaccine (RZV), was approved in the United States (US) in October 2017 for the prevention of HZ infection in adults 50 years and older who are immunocompetent. It was subsequently approved (July 2021) for use in adults 18 years and older who are or will be at increased risk of HZ due to immunodeficiency or immunosuppression caused by known disease or therapy. In adults with weakened immune systems, RZV was between 68% and 91% effective in preventing HZ, depending on their underlying immunocompromising condition.⁸ RZV is a 2 dose vaccine; it is recommended that the second RZV dose be given 2 – 6 months after the first, or 1 – 2 months after the first if needed among people with weakened immune systems.⁹

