 Non-tofacitinib exposed person-time
★ First RZV administration
★ Second RZV administration

[figure not shown]
9.2.3.2.1.2. Comparator 2-Dose Cohorts

In a similar fashion to the identification of the RZV 2-Dose cohorts, Optum will identify a cohort of patients without exposure to RZV among patients who are current users of tofacitinib. To minimize the immortal time bias that may be introduced when exposure is defined based on information accrued during follow-up,¹⁴ these patients will be randomly drawn from time-matched vaccination risk sets that are defined as sequential 4-week windows during which they were eligible for inclusion in the RZV cohorts, but without any RZV exposure during the window. Matching within this narrow caliper of calendar time limits the potential immortal time introduced by using future information (ie, lack of RZV receipt) to classify patients at the time of cohort entry. A cohort entry date will be randomly selected from this time window. In addition, other factors, such as duration of tofacitinib use, will be considered for matching upon feasibility, which will be described in the statistical analysis plan (SAP).

To construct the vaccination risk sets, separate 4-week windows will be created, starting on the study initiation date (20 October 2017) through the end of the study period. Among patients who are current tofacitinib users within a given 4-week window, patients without any RZV exposure who meet the study inclusion criteria (Section 9.2.1) and exclusion criteria (Section 9.2.2) at the beginning of the 4-week window will be identified. These patients will be eligible to be sampled as comparator patients for each RZV initiator identified with receipt of a second RZV dose during the same 4-week window. For example, as illustrated in Figure 4, patient A at the time of second RZV dose was eligible to be matched to comparator patient B and D during risk set #1, and similarly, patient B at the time of second RZV dose was eligible to be matched to comparator patient D and E during risk set #2.

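### The recent-user sensitivity analysis pools current and recent tofacitinib users with no estimate by recency, so its agreement with the main result says little about carry-over after discontinuation

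*Protocol*

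**What the plan says.** Section 9.7.4 creates a second set of vaccinated cohorts and "matched comparator cohorts that include current tofacitinib users and recent tofacitinib users within given time intervals, such as 8 weeks, preceding cohort entry". In the 2-dose analysis a vaccinee qualifies with the "second dose occurring during a tofacitinib on-treatment period or 8-week recent-treatment period"; the first dose in the ≥ 1 dose analysis is handled likewise. Each vaccinated cohort is "time-matched to comparators who also meet the definition of current or recent user of tofacitinib". The recent period is defined as "starting on the day following the end of the on-treatment period", that is, after days' supply plus the 30-day grace period. It lasts 8 weeks, and the protocol allows a shorter or longer window depending on sample size.

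Several aims are given. One is size: "The inclusion of recent tofacitinib users will maximize sample size". Another is breadth of real-world use. A third is to "address the potential for extended immunosuppressant effects of tofacitinib following discontinuation". The analysis covers both the HZ and the flare outcomes.

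No estimate restricted to recent users, and no split by current versus recent status at entry, is described in Section 9.7.3.1 or Section 9.7.4.

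**The concern.** Carry-over is a question about effect modification: is the vaccine as impaired shortly after tofacitinib stops as it is on treatment? Answering it needs effectiveness in recent users set beside effectiveness in current users. The planned analysis instead adds recent users to the patients already eligible for the main analysis. If they are a minority, the pooled estimate stays close to the main one under either answer. A reader who sees agreement may take it as confirmation that patients vaccinated after stopping respond like those on drug.

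The protocol uses the better design for a parallel question. In the same section, prior Zostavax vaccination is examined in separate strata and judged by how far the estimates differ.

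A secondary issue is balance. In the main analysis everyone is a current user at entry. Here status can differ between vaccinees and comparators, and Section 7 reports that "Increased rates of HZ have been observed in patients treated with tofacitinib compared to patients receiving placebo".

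**Working it through.** The protocol gives no figure for this analysis, so there is none to reproduce. The check asks how far the pooled estimate moves between full carry-over and none.

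**Inputs from Section 9.5 and Figure 6.** HZ rate 1.2 per 100 person-years; 2:1 comparators; effectiveness (VE) without tofacitinib 85%; illustrative VE on tofacitinib 66.7% at 2,000 vaccinated person-years; median 11 tofacitinib dispensings among 2-dose recipients.

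**Assumptions.** The recent-user share f is not given. I assume 11 fills of 30 or 90 days, 1 to 3 treatment episodes (e), and vaccination spread evenly over eligible time. Each episode adds 30 grace days and 56 recent days, so recent use reaches 30 + 56 = 86 days past the end of supply.

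f = 56e / (11 × supply + 86e)

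- 90-day fills, e = 1: 56 / 1,076 = 5.2%
- 30-day fills, e = 1: 56 / 416 = 13.5%
- 30-day fills, e = 2: 112 / 502 = 22.3%
- 30-day fills, e = 3: 168 / 588 = 28.6%

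**Dilution.** With equal background HZ rates and f balanced between cohorts, pooled VE = (1 − f) × VE(current) + f × VE(recent). With no carry-over, VE(recent) is set to 85%.

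| f | Pooled VE, current 66.7% | Shift (points) | Pooled VE, current 40% | Shift (points) |
|---|---|---|---|---|
| 5.2% | 67.7% | 1.0 | 42.3% | 2.3 |
| 13.5% | 69.2% | 2.5 | 46.1% | 6.1 |
| 22.3% | 70.8% | 4.1 | 50.0% | 10.0 |
| 28.6% | 71.9% | 5.2 | 52.9% | 12.9 |

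With full carry-over, VE(recent) = VE(current) and the shift is 0.

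**Against sampling error.** At 2,000 vaccinated person-years and VE 66.7%, expected cases are 0.012 × 2,000 × 0.333 = 8.0 vaccinated and 0.012 × 4,000 = 48 comparator. SE of the log rate ratio = √(1/8.0 + 1/48) = 0.382. The Wald 95% interval for VE is 29.6% to 84.3%. At VE 40% it is −8% to 67%. Every pooled value above lies inside the corresponding interval.

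The two estimates share most of their patients, so the fairer yardstick is the SD of their difference on the log scale, √(v − w), with v and w the main and pooled variances. At VE 66.7% the log shifts are 0.029, 0.077, 0.131 and 0.171 against SDs of 0.064, 0.105, 0.138 and 0.158, which is 0.5 to 1.1 SD. At VE 40% the range is 0.9 to 2.2 SD. Only a wide effectiveness gap together with a large recent share would be noticeable. All of this is before the required split into UC and RA.

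**What a stratum would hold.** Recent-user vaccinated person-years = 2,000 × f / (1 − f), about 110 at f = 5.2% and 800 at f = 28.6%. At VE 85% that gives 0.2 to 1.4 vaccinated HZ cases against 2.6 to 19 comparator cases.

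**Status imbalance.** Suppose recent users have 0.5 or 0.7 times the HZ rate of current users (assumption), true VE is 66.7% in both, and recent shares after weighting are 10% in one arm and 20% in the other. With 10% among vaccinees and ratio 0.5, VE = 1 − 0.333 × 0.95 / 0.90 = 64.9%. Reversed, it is 68.5%. With ratio 0.7 the values are 65.6% and 67.7%. The distortion is 1.0 to 1.9 points.

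**The case against.** The strongest reply concerns purpose. Carry-over is only one of several aims, and a widened, pooled cohort is a legitimate robustness check for sample size and real-world use. That stands, and the pooled estimate should stay. It does not rescue the carry-over aim, which the protocol states in its own right.

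Second, Section 9.7.4 is silent on further strata rather than ruling them out, and it leaves room for additional analyses. That is fair, but no planned analysis fills the gap. Both subgroups in Section 9.7.3.1 require current use at the second dose. The continued-exposure analysis classifies patients by exposure after entry. Dropping the grace period is applied to the main cohorts and is only to be considered.

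Third, a reader might infer that the comparison is confounded because comparators are not matched on status. The documents do not support that. Section 9.2.3.2.1.2 says "other factors, such as duration of tofacitinib use, will be considered for matching upon feasibility" and defers details to the SAP. Average tofacitinib dose over 91 days and cumulative dose over 365 days are propensity-score candidates (Section 9.3.6.4), and variables still imbalanced after weighting enter the outcome model (Section 9.7.2). The planned model is weighted Cox regression, not an analysis within matched pairs, so a mixed pair does no harm in itself. Control is partial, however: 22 mg/day stopped 45 days before entry averages 22 × 46 / 91 = 11.1 mg/day, about the same as uninterrupted 11 mg/day.

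Fourth, a recent-user stratum would be nearly uninformative for HZ. That is true. It argues for reporting the stratum with its interval or withdrawing the aim, not for letting the pooled figure stand in.

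**Conclusion.** The concern holds in a limited form. As written, the analysis pools current and recent users and plans no estimate by recency, so it does not deliver on the carry-over aim. With recent users at an assumed 5% to 29% of the cohort and the protocol's 66.7% and 85%, opposite answers on carry-over differ by 1.0 to 5.2 points, about one SD of the difference or less. The 85% in recent users is the extreme case of no carry-over; partial carry-over would shift the estimate less.

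A reader might go further and infer that the pooled result must agree with the main one by construction. That depends on a share the protocol does not give. At 50% recent users the shift would be about 9 points, and with VE 40% in current users and a 29% share it would be 12.9 points. The defensible statement is conditional: unless recent users are a large share, agreement is not evidence on carry-over. No primary or secondary estimate is affected. Flare has the same design gap, but the protocol gives no flare rate from which to size it.

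**What to change.** - Keep the pooled estimate and present it for sample size and real-world use.
- Add HZ and flare estimates by tofacitinib status at cohort entry (current, recent), each against comparators of the same status, with confidence intervals and labelled descriptive.
- State that agreement between the pooled and main estimates is not evidence on carry-over. If the recent stratum has too few events to report usefully, drop the statement that the analysis addresses extended immunosuppression.
- In the pooled analysis, include status at entry in the propensity score or at least in the balance check.

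The cost is a few sentences in the protocol or SAP, one added status variable and two stratum estimates from the same data. The recent-user stratum will be small and imprecise, above all for HZ, and some recent vaccinees may find fewer than two comparators of the same status. A formal interaction test would have almost no power for HZ and should not be relied on.

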9.3. Variables

9.3.1. Exposure to Tofacitinib

Tofacitinib treatment will be identified through the presence of National Drug Codes (NDCs) on pharmacy claims. In addition to dispensings of tofacitinib, other variables, such as duration of treatment and dose, will also be assessed as detailed in Section 9.2.3.1.

Tofacitinib will be assessed through the presence of the following NDCs in pharmacy claims:

- NDC 00069050114 XELJANZ XR 11 mg extended-release tablet;
- NDC 00069050130 XELJANZ XR 11 mg extended-release tablet;
- NDC 00069050230 XELJANZ XR 22 mg extended-release tablet;
- NDC 00069100101 XELJANZ 5 mg tablet;
- NDC 00069100201 XELJANZ 10 mg tablet;
- NDC 00069102901 XELJANZ 1 MG/ML oral solution;
- NDC 00069102902 XELJANZ 1 MG/ML oral solution.

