9.3.6.4. Treatment History

- Tofacitinib treatment;
 - Tofacitinib dose;
 - Average daily dose in prior 91 days;
 - Cumulative dose in prior 365 days;
 - Treatment duration;
- Zostavax[®] vaccination;
- TNF inhibitor treatment (eg, etanercept, adalimumab, golimumab, infliximab, certolizumab);
- Non-TNF biologics (eg, abatacept, rituximab, tocilizumab, sarilumab, anakinra, ustekinumab, vedolizumab);
- csDMARD treatment (eg, methotrexate, sulfasalazine, hydroxychloroquine, leflunomide, azathioprine);
- Immunosuppressants (eg, azathioprine, 6-mercaptopurine, cyclosporine);
- JAK inhibitor treatment (eg, baricitinib, upadacitinib);
- Corticosteroid treatment;
 - Average daily dose (eg, None, ≤ 5 mg/day, >5 to ≤ 10 mg/day, >10 to ≤ 20 mg/day, and >20 mg/day of prednisone average dose equivalent);
 - During 30 days prior to cohort entry;
 - During 365 days prior to cohort entry;
- Number of treatments for UC/RA prior to cohort entry;
- Chemotherapy;
- Radiotherapy;
- 5-aminosalicylates (eg, mesalamine, balsalazide, olsalazine);
- Ozanimod.

Additional therapies that are approved for the treatment of UC or RA may be incorporated if they become available. All of the above covariates may be considered for inclusion in the propensity score model used for IPTW.

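### A median split of daily tofacitinib dose need not separate the dose levels, so the dose-response sensitivity analysis should use strata defined by dose level

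*Protocol*

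**What the plan says.** Protocol Section 9.7.4 gives the purpose as "To assess a potential dose-response relationship between tofacitinib exposure and study outcomes". It then fixes the method: "the daily dose of tofacitinib will be calculated based on dispensings received in the 91 days prior to cohort entry", after which "the cohorts will be stratified according to high versus low dose of tofacitinib based on the median daily dose". Nothing in that paragraph passes the choice of cut to the SAP, whereas the same section does so for the alternative flare definitions. A second stratification, by cumulative dose over 365 days, is planned without a stated cut-point.

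Section 9.3.1 lists the products that count as tofacitinib. The tablets are "NDC 00069100101 XELJANZ 5 mg tablet", "NDC 00069100201 XELJANZ 10 mg tablet", "NDC 00069050130 XELJANZ XR 11 mg extended-release tablet" (the 11 mg XR strength has two codes) and "NDC 00069050230 XELJANZ XR 22 mg extended-release tablet". A 1 mg/mL oral solution is also listed.

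The protocol gives no dosing frequency, no share of patients by strength or formulation, and no denominator for daily dose. Sections 9.7.3.1 and 9.7.3.2 state that UC and RA are analysed separately.

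**The concern.** A dose-response analysis needs strata that differ in dose. A median cut guarantees only that patients are ranked on the measured value. With a few product strengths, the measured dose clusters into two levels, with a small formulation difference inside each. Where most patients are on one level, the median falls inside that cluster, and what divides the strata may be formulation, the placing of tied values or the number of fills.

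Section 7 of the protocol gives the motivation for the study: tofacitinib's immunosuppressive effect might weaken the vaccine's protection. An analysis by tofacitinib dose bears on that directly. If both strata hold nearly the same dose, a null result could be misread as absence of dose-response, and a difference could be due to formulation or refill behaviour.

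**Working it through.** The protocol states no median, dose mix or stratum size for this analysis, so there is no figure to reproduce. The check asks what the rule does over a range of mixes.

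**1. A bound that needs no dosing assumption.** Let p be the share on the higher level. If the cut gives equal halves, the high stratum holds 50% of patients, of whom at most p are on the higher level. The lower-level share of the high stratum is then at least (0.5 − p)/0.5 = 1 − 2p.

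- p = 2%: 1 − 0.04 = 96%
- p = 10%: 1 − 0.20 = 80%
- p = 30%: 1 − 0.60 = 40%

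**2. When tied values make the strata unequal.** Assumption, not in the protocol: immediate-release (IR) tablets are taken twice daily and XR once daily. The possible values are then 2 × 5 = 10, 11, 2 × 10 = 20 and 22 mg/day. Let x be the XR share, taken as independent of dose level. Lower-level IR patients make up (1 − p)(1 − x).

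- The median is 10 if (1 − p)(1 − x) exceeds 50%.
- It is 11 if that product is below 50% and 1 − p is above 50%.
- It is 20 or 22 if p exceeds 50%.

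| p | x | Lower-level IR | Median | Ties placed low: high stratum | Ties placed high: high stratum |
|---|---|---|---|---|---|
| 2% | 40% | 0.98 × 0.60 = 58.8% | 10 | 41.2% of patients; 2/41.2 = 4.9% on higher level; (39.2 + 0.8)/41.2 = 97.1% XR | everyone; low stratum empty |
| 2% | 60% | 0.98 × 0.40 = 39.2% | 11 | 2% of patients; all on higher level | 60.8%; 2/60.8 = 3.3% on higher level; (58.8 + 1.2)/60.8 = 98.7% XR |
| 30% | 40% | 0.70 × 0.60 = 42.0% | 11 | 30%; all on higher level | 58.0%; 30/58 = 51.7% on higher level |
| 30% | 60% | 0.70 × 0.40 = 28.0% | 11 | 30%; all on higher level | 72.0%; 30/72 = 41.7% on higher level |
| 60% | 60% | 0.40 × 0.40 = 16.0% | 20 | 36%, all 22 mg XR; low stratum 24/64 = 37.5% on higher level | 60%; all on higher level |

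The split is exact when the median is 11 with ties low, or 20 with ties high. In the other cells it mixes levels, or leaves one stratum empty. In the first row, where a comparison is possible, the contrast is almost wholly XR against IR (11 against 10 mg/day).

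**3. Refill timing, only if daily dose is mg dispensed divided by 91.**

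- 10 mg/day, three 30-day fills: 900/91 = 9.89; four fills: 1,200/91 = 13.19.
- 11 mg/day, three fills: 990/91 = 10.88; four fills: 1,320/91 = 14.51.
- 10 mg/day, two 90-day fills: 1,800/91 = 19.78. This equals a patient on 20 mg/day with three 30-day fills (1,800/91 = 19.78).

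If the denominator is total days' supply, each patient returns to 10, 11, 20 or 22 and this source of misclassification disappears. The formulation and tie effects in step 2 remain.

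**The case against.** The strongest reply is that the failure is conditional on figures the protocol does not contain. With daily dose per day of supply and ties placed low, three of the first four rows of the table isolate the higher level exactly. In the 2%/60% XR row the only weakness is a small stratum, which dose-level strata would share. UC and RA are analysed separately and may have different mixes. The denominator and the tie rule are details that an SAP commonly settles, so their absence is no fault of the protocol. All of this stands.

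A reader might infer more: that the rule always separates XR from IR rather than high from low dose, that refill timing certainly distorts it, or that this is the only planned look at the amount of tofacitinib. The documents support none of these. Where the higher level is a sizeable share (about 20% to 60%), the same cut can work, depending on ties. The refill effect rests on a denominator that Section 9.7.4 does not state. That section also plans strata by cumulative dose and by continued exposure during follow-up, and Section 9.7.3.1 separates patients on tofacitinib at both vaccine doses from those on it at the second only.

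What the reply does not remove is that, when the median cut succeeds, it does so through the mix and the tie rule. Strata defined by dose level would be the same in those cases and would remain interpretable in the others.

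**Conclusion.** The point holds in conditional form. The protocol fixes a median cut for a dose-response question, although the listed tablets come in two strengths per formulation, and the cut need not separate those levels. With roughly equal halves, at least 96%, 80% or 40% of the high stratum is on the lower level when 2%, 10% or 30% of patients are on the higher one. This bound rests on no dosing-frequency assumption.

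The further statement, that strata mainly reflect XR against IR or the placing of ties where one level predominates, assumes twice-daily IR and once-daily XR use. The true mix in each disease cohort is unknown from the protocol. The primary comparison and the secondary estimates are not affected. This is an inexpensive improvement to a sensitivity analysis.

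**What to change.** In Section 9.7.4, replace the median cut with dose-level strata.

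- Assign each patient by the product and strength of the dispensing that covers cohort entry. Section 9.4.1 lists drug code, dosage form, strength, fill date and days of supply among the pharmacy fields.
- Map XR, IR and oral-solution products to a common dose level, for analysis only. The protocol contains no such map, so the sponsor must supply one in a short table. Strength alone will not classify the oral solution, so the table must say how it is assigned.
- Apply the same rule to comparators, separately in UC and RA.
- State that dose-response is not assessable in a disease cohort where one level is too rare.
- Keep the 365-day cumulative-dose strata, but interpret them as mixing dose, duration and adherence. The covariate "Average daily dose in prior 91 days" in Section 9.3.6.4 can stay as it is.

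The cost is a wording change and a small mapping table. Strata may be unequal in size, so one will be estimated less precisely.
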